# **Effects of Hypopressive Exercise Associated With Strength and Resistance Training in the Management of Fatigue, Urinary Incontinence Symptoms, Sexual Function and Quality of Life in Women Treated for Gynecological Cancer**

## **Study Protocol (23-08-2021)**

### **Research design**

[figure not shown]
Experimental, single-blind randomized clinical trial type.

### **Determination of sample size**

The sample size was calculated using the GPower version 3.1 software, considering a size of effect, Cohen's  $d$  of 0.2, to achieve a power of 80%, with a significance level of 5%. was used the analysis of variance of repeated measures, considering interaction between and within groups using 2 measurements. Thirty-six participants (18 per group) were suggested.

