### **Statistical Analysis**

Statistical analysis will be performed using a statistical package SPSS (version 17.0). The data will be expressed as mean, standard deviation (SD), lower and upper limit of the confidence interval (CI, 95%) or median, minimum, maximum, first and third quartile, according to normality distribution using the Kolmogorov Smirnov test. To assess fatigue, symptoms of urinary incontinence, sexual function and quality of life, a two-way mixed analysis (two-way ANOVA) will be performed, considering time (pre-intervention and post-intervention) as an intra-subject and group factor as a between-subjects factor. The significance level will be set at .05 for all statistical analyses. The intragroup effect sizes for the aforementioned variables will also be calculated using the Cohen d index. An effect size of more than 0.8 will be considered large, approximately 0.5 moderate, and less than 0.2 small (Cohen, 1988).

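### Thirty-six women do not give 80% power at Cohen's d = 0.2; at pre-post correlations of 0.3 to 0.8 power is 8-15% or 17-45%, depending on how d is converted

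*Combined protocol and SAP*

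**What the plan says.** The section on determination of sample size names G*Power 3.1 and a repeated-measures analysis of variance, "considering interaction between and within groups using 2 measurements". The effect size is a Cohen's d "of 0.2, to achieve a power of 80%, with a significance level of 5" per cent. The result is: "Thirty-six participants (18 per group) were suggested".

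The Statistical Analysis section plans the matching test for fatigue, incontinence symptoms, sexual function and quality of life: "a two-way mixed analysis (two-way ANOVA) will be performed, considering time (pre-intervention and post-intervention) as an intra-subject" factor, with group as the between-subjects factor. The power statement therefore applies directly to the planned time-by-group test. The same section uses Cohen's d in its usual sense and puts 0.2 at the small end of the scale.

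The document does not give the pre-post correlation, the conversion from d to the f that this type of G*Power calculation uses, the outcome and SD behind the 0.2, or an allowance for dropout.

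**The concern.** A standardised effect of 0.2 is small, and 18 women per group is a small trial. Measuring each woman twice helps only as far as the two measurements are correlated, and ordinary correlations do not close a gap this wide.

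The paragraph is the only justification given for 36 women. Taken at face value, it promises a 20% chance of missing an effect of d = 0.2. If that is untrue, a null result could be misread as evidence against small effects. Without the index and correlation that were entered, a reader cannot tell what effect the trial was sized for.

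**Working it through.** **Inputs from the document.** N = 36 (18 per group), 2 groups, m = 2 measurements, significance level 5%, target power 80%, effect 0.2 labelled Cohen's d. The F test is non-directional, so I treat the level as two-sided.

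**Assumed input.** Pre-post correlation ρ: not stated; range 0.3 to 0.8.

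**Formula.** For the 2 × 2 time-by-group interaction, power comes from the noncentral F distribution with 1 and N − 2 = 34 degrees of freedom and

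λ = f² × N × m / (1 − ρ).

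At 34 degrees of freedom, 80% power needs λ of about 8.32. (At ρ = 0.5 the required f is 0.2403, and 0.2403² × 72 / 0.5 = 8.32.)

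**Attempt to reproduce 36 with 0.2 as Cohen's d.** There are three readings of d:

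- (a) d is the between-group difference in change divided by the raw SD. The interaction effect in each of the four cells is then a quarter of that difference, so f = 0.2/4 = 0.05 and λ = 0.0025 × 72 / (1 − ρ) = 0.18 / (1 − ρ).
- (b) The generic conversion f = d/2 = 0.10, so λ = 0.01 × 72 / (1 − ρ) = 0.72 / (1 − ρ).
- (c) d is the difference in change divided by the SD of the change score. This is a two-sample t test on change with noncentrality 0.2 × √(18/2) = 0.6 on 34 degrees of freedom; ρ does not enter.

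| ρ | (a) power, N = 36 | (b) power, N = 36 | (c) power, N = 36 |
|---|---|---|---|
| 0.3 | 7.8% | 16.7% | 9.0% |
| 0.5 | 9.0% | 21.5% | 9.0% |
| 0.65 | 10.7% | 28.6% | 9.0% |
| 0.8 | 15.2% | 45.4% | 9.0% |
| 0.9 (beyond the assumed range) | 25.6% | 74.1% | 9.0% |

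Total N for 80% power at ρ = 0.3, 0.5 and 0.8:

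- (a) 1102, 788 and 316
- (b) 278, 200 and 82
- (c) 788 at any ρ

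A simulation of t tests on change (40,000 trials, 18 per group) at ρ = 0.3, 0.5 and 0.8 gave 7.8%, 9.0% and 15.0% for (a), and 17.0%, 21.4% and 45.1% for (b).

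**Correlation that would rescue 36.** Setting λ = 8.32 gives ρ = 1 − 0.18/8.32 = 0.978 under (a) and ρ = 1 − 0.72/8.32 = 0.913 under (b). No value works under (c).

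**One-sided testing.** Using α = 0.10 as the one-sided equivalent raises power only to 14.2-24.2% under (a) and 26.2-58.5% under (b) over ρ = 0.3 to 0.8.

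**Routes that do give 36.**

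- 0.2 entered as f: λ = 0.04 × 72 / (1 − ρ) = 2.88 / (1 − ρ). This reaches 8.32 at ρ = 0.654, and 36 is the smallest even N reaching 80% only for ρ from 0.654 to 0.674. At ρ = 0.65 power is 79.6%; at ρ = 0.5 the required N is 52.
- 0.2 entered as partial eta-squared: f = √(0.2/0.8) = 0.5. Under the option λ = f² × (N − 2), N = 36 gives λ = 0.25 × 34 = 8.5 and power 80.8%; N = 34 gives 78.3%.

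**What 18 per group detects with 80% power.** In SDs of the change score: √8.32 / √(18/2) = 2.88/3 = 0.96. In raw SDs, multiply by √(2(1 − ρ)): 1.14, 0.96, 0.80 and 0.61 at ρ = 0.3, 0.5, 0.65 and 0.8.

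**The case against.** The strongest reply is that the calculation may have been right and only its label wrong. This type of G*Power calculation takes f, not d. If 0.2 went in as f with a correlation near 0.65-0.67, or as partial eta-squared, 36 follows. The miss rates computed for d = 0.2 would then not describe the effect the investigators had in mind. This stands as far as it goes: the document cannot show that the trial is underpowered for its intended effect. It does not save the text. On either route the stated Cohen's d of 0.2 is wrong, and the effect sized for is much larger: f = 0.2 is a difference in change of 0.2 × 4 = 0.8 raw SD, or d = 0.4 under the f = d/2 convention. The f route also needs a narrow, unreported band of correlation, and neither route is documented.

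A second reply is that the correlation is unstated, so under readings (a) and (b) the failure is conditional. That is correct. The condition is a correlation of at least about 0.978 or 0.913, for which the document offers no support. If such a value was used, the whole sample size rests on it and it has to be reported.

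**Conclusion.** The sample-size statement is wrong as written and must be corrected. Over assumed correlations of 0.3 to 0.8, the chance of missing d = 0.2 with 36 women is 85-92% under (a) and 55-83% under (b); under (c) it is 91% at any correlation. The paragraph implies 20%. Even the most favourable of these cases needs 82 women, more than twice the planned number. The figures assume a two-sided 5% test and all 36 women analysed; any dropout lowers power further.

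Confidence is high that the stated index, power and sample size do not match. Which index and correlation produced 36 cannot be determined from the document.

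**What to change.** Keep 36 women and remove the claim of 80% power for Cohen's d = 0.2. Report the effect-size index, the G*Power effect-size option and the correlation actually entered. Then state what the sample can detect, for example:

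> With 18 women per group and a two-sided 5% level, the time-by-group test has 80% power for a between-group difference in pre-post change of 0.96 SD of the change score. In raw SD units this is 1.14, 0.96, 0.80 or 0.61 if the pre-post correlation is 0.3, 0.5, 0.65 or 0.8. These figures assume that all 36 women are analysed.

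The cost is rewording one paragraph and retrieving the G*Power inputs; no extra women are needed and the planned analysis does not change. The drawback is that the stated detectable effect becomes less favourable. If the inputs cannot be found, the origin of 36 should be reported as unknown.

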### **Randomization and blinding**

Participants will be assigned randomly assigned to one of the two groups studied (Hipopresive exercise group, HEG; conventional exercise group, CEG). Randomization will be performed by a member of the team, blinded to the study protocol. A computer program will be used to perform the randomization (<https://www.graphpad.com/quickcalcs/randomize1.cfm>). Both groups will receive 4 weeks of supervised training with a frequency of three times a week, with an approximate duration of 60 minutes each session. Figure 1 presents the flowchart with the experimental design of the study.

**Figure 1.**

### **Protocol of therapeutic exercise**

Both groups of exercises will train three times a week, twice in a synchronous online way and once in an asynchronous way, considering a standardized exercise guide. In all of the intervention sessions, the conventional exercises will be guided by the standardized exercise guide previously developed by the team of the study for 4 weeks. Each session will last approximately 60 minutes. In all sessions, exercise perception (using the Borg scale), respiratory rate and heart rate will be monitored, considering instructions via remote. For aerobic training, a light to moderate intensity will be considered (Borg 9-13). Resistance exercises will be carried out using large muscle groups and the participants' body weight. All the exercise sessions will be the same for the groups and will begin with a five-minute warm-up with exercises that involve large muscle groups in a perceived exercise rating of 10 to 12 on the Borg scale and the sessions conclude with a 10 minutes that include dynamic and static muscle stretching activities of the main muscle groups worked in the session. In the first week of training, a familiarization with the perception of perceived effort will be carried out using the Borg scale.

The strength training will consist of 3 sets of 8-12 repetitions of 8 exercises, using leg extensions and lower limbs, biceps curls and extensions, lunges, chest curls, abdominal curls, shoulder curls and back extension. Participants will perform exercises without charge in all sessions. The training progress will be related to the increase in volume according to what corresponds to each week: a) weeks 1 and 2 (3 sets of 8 repetitions, adaptation weeks), b) week 3 (3 sets of 10 repetitions) and c) week 4 (3 sets of 12 repetitions).

### **Hypopressive Exercise Protocol**

The hypopressive exercises will be carried out by the GEH group at the end of the strength and resistance training session. It will be considered the static hypopressive exercise in the supine position, with a variant of arms in flexion, abduction and extension, consisting of 3 exercises. The dosage will consist of 3 series of each exercise, using a protocol adapted from the previous study by Cabañas and Chapinal. Participants must perform 3 cycles of deep inspiration (nose) and forced breathing (mouth). After the last breath, the participants will be instructed to maintain the position performing 3 cycles of normal breathing, without performing the apnea, to guarantee the safety of the user and that the intervention is remote. During the breathing phase, participants will be instructed to perform pelvic floor contraction. The procedure must be repeated 3 times in each variant of arms.

### **Recruitment**

Participants will be recruited through the referral of a medical oncologist from the Regional Hospital of Talca in Chile. Potential study participants will be called for an initial evaluation where eligibility will be determined and the objectives of the research will be explained. Participants who agree to participate must sign an informed consent.

### **Generation and hiding of sequences**

After selecting the sample and performing the baseline evaluations, the participants will be randomly assigned to one of the two study groups. Randomization will be performed by a member of the team, blinded to the study protocol. A computer program will be used to perform the randomization (<https://www.graphpad.com/quickcalcs/randomize1.cfm>). Both groups will receive 4 weeks of supervised training with a frequency of three times a week, with an approximate duration of 60 minutes each session. Figure 1 presents the flowchart with the experimental design of the study.

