### **Data collection**

Standardized forms will be used to record pre- and post-intervention evaluations. The registry will consider demographic data, social and health habits, clinical variables: comorbidities, blood pressure, body mass index (weight, height), type of gynecological cancer, cancer staging and type of oncological treatment. In addition, the dosage of the kinesthetic intervention will be recorded according to the Borg scale for each session.

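### Cancer type, stage and treatment are recorded before allocation but used in neither randomization nor model, which costs some precision and leaves no planned response to a visible imbalance

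*Combined protocol and SAP*

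**What the plan says.** - **Allocation.** Both Randomization and blinding and Generation and hiding of sequences name a web randomizer: "A computer program will be used to perform the randomization". Neither section mentions strata, blocks or minimisation. The second places assignment after the baseline evaluations.
- **Baseline data.** Data collection lists among the recorded variables "type of gynecological cancer, cancer staging and type of oncological treatment".
- **Model.** Statistical Analysis uses time (pre, post) within subjects and "group factor as a between-subjects factor". It names no covariate and no adjusted or sensitivity analysis.
- **Size and target.** Determination of sample size plans on a repeated-measures ANOVA "considering interaction between and within groups using 2 measurements", and concludes: "Thirty-six participants (18 per group) were suggested".

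**The concern.** The title admits women treated for gynecological cancer in general, so types, stages and treatments may be mixed. The protocol does not give the mix. At 18 per arm, chance alone can leave the arms visibly different on one of these factors. If that factor affects how much women change over the 4 weeks, part of the observed arm difference in change comes from the imbalance.

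The plan holds the information needed to limit this, since the factors are recorded and assignment follows the baseline evaluations. It uses them neither before assignment nor in the analysis. If the baseline table shows unequal treatment types, the plan offers no agreed response. Any adjustment would then be chosen with the data in hand, across four outcome domains: fatigue, incontinence symptoms, sexual function and quality of life.

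**Working it through.** **Inputs from the protocol:** N = 36, 18 per group; one pre and one post measurement; model with time and group. **Assumptions, because the protocol gives no figures:** prevalence of a binary factor from 25% to 50%; effect g of the factor on change of 0.3, 0.5 or 0.8 SD, where SD is the standard deviation of change among women with the same factor level.

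**1. Which differences survive the group-by-time test.** With two measurements, the interaction estimate is mean change in one arm minus mean change in the other. A factor that adds the same amount at both times drops out of each woman's change. A factor that moves change by g shifts the arm difference by g × D, where D is the difference between arms in the proportion with the factor. For the same reason, adding only a factor main effect cannot alter the interaction test. A factor-by-time term is needed.

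**2. How large D can be.** Take an exact 18/18 split with K of the 36 women carrying the factor. The number X in one arm is hypergeometric, and D = (2X − K)/18.
- K = 18: P(X = 9) = 0.2605 and P(X = 8) = P(X = 10) = 0.2110. So P(|D| ≥ 4/18, or 22 points) = 1 − 0.2605 − 2 × 0.2110 = 0.318. P(|D| ≥ 6/18) = 0.094.
- K = 12: P(X = 6) = 0.2753 and P(X = 5) = P(X = 7) = 0.2178. So P(|D| ≥ 4/18) = 1 − 0.2753 − 2 × 0.2178 = 0.289. P(|D| ≥ 6/18) = 0.075.
- K = 9: P(|D| ≥ 4/18) = 0.121.
- At least one of three independent factors, each present in half the women, out of balance by 22 points or more: 1 − (1 − 0.318)³ = 0.68.

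If the draw is also unrestricted, which the text does not say, an exact 18/18 split has binomial probability 0.13 and a split of 22:14 or worse 0.24.

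**3. Error rate.** In 40,000 simulated trials that ignored a factor, the unadjusted test rejected a true null in 5.0% of trials (g = 0.5) and 4.8% (g = 0.8). Among allocations with |D| of 20 points or more, the rate was 6.3% and 7.8%. Among the rest it was 4.3% and 3.3%.

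**4. Precision gained.** For K = 18, Var(X) = 18 × ½ × ½ × 18/35 = 2.314, so Var(D) = 4 × 2.314/324 = 0.02857. Without stratification or adjustment, the variance of the arm difference is 2/18 + 0.02857 g². With balanced strata and the factor in the model it is 2/18 = 0.1111.

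| g (assumed) | Unstratified, unadjusted | Stratified, adjusted | Reduction |
|---|---|---|---|
| 0.3 | 0.1137 | 0.1111 | 2.3% |
| 0.5 | 0.1183 | 0.1111 | 6.0% |
| 0.8 | 0.1294 | 0.1111 | 14.1% |

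For K = 12, Var(D) = 0.0254 and the reductions are 2.0%, 5.4% and 12.8%. I also fixed a treatment effect at which the stratified, adjusted test has 80% power. The unstratified, unadjusted test then has about 77% (g = 0.5) and 74% (g = 0.8) by simulation.

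**5. Model term without stratification.** The variance becomes 0.1111 × E[1/(1 − D²)] for K = 18. The expectation is 1.031, giving 0.1146. Against the middle column of the table this is 0.8% higher at g = 0.3, 3.1% lower at g = 0.5 and 11.4% lower at g = 0.8.

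**6. Cost if the factor is irrelevant.** Take interaction f = 0.2 and pre-post correlation 0.64 (assumed). Then λ = 36 × 0.2² × 2/(1 − 0.64) = 8.0, and power is 78.5% on 34 df. One df for a balanced stratum leaves 78.4%. Without stratification, λ/1.031 on 33 df leaves about 77%.

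**The case against.** The strongest reply is that nothing here is an error. Simple randomization is valid, chance imbalance is not bias, and the overall error rate holds. The interaction test already removes differences in symptom level due to cancer type, stage or treatment. At g = 0.5 the gain of 6% is worth about two women (36 × 0.06 = 2.2). The protocol gives no evidence that any of these factors predicts change in any outcome, and one that matters for pelvic symptoms may not matter for fatigue or quality of life. All of this stands, and it limits the point to a low-cost improvement.

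A reader might go further and infer that a distortion worth half the planned effect is likely and would go uncorrected. The documents do not support that.
- **Likely.** With Cohen's d of 0.2 taken literally, half the effect is 0.1 SD. At g = 0.5 a 22-point imbalance gives 0.5 × 4/18 = 0.11 SD, but the chance of a shift of at least 0.1 SD, in either direction, is 12 to 32% for prevalences of 25 to 50%. At g = 0.3 it is 2 to 9%. It passes one half for a single factor only when g is about 1 SD, at prevalences of a third or more.
- **Half the planned effect.** The benchmark is unstable. Thirty-six women do not follow from d = 0.2: read as f = 0.1 with correlation 0.5, 36 gives 21% power and 200 are needed. An input of f = 0.2 comes closer, reaching 36 at a correlation of about 0.65. That is a difference in change of 4 × 0.2 = 0.8 SD, so half is 0.4 SD. For one factor with g up to 1 SD the chance of such a shift is at most 2%. The sample-size basis is a separate and larger matter.
- **Uncorrected.** Constant level differences cancel. Only effects on change remain.

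**Conclusion.** The point holds as a modest gap in design and pre-specification. The plan records three plausible prognostic factors in time to use them, and uses none. A visible imbalance in a given factor is plausible, at about 30% for one present in a third to a half of the women and 12% for one present in a quarter. The plan does not say what would then be done. The consequence is some lost precision and a conditional error rate of roughly 6 to 8% in unlucky allocations, balanced by less than 5% in the others.

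The imbalance probabilities need only the 18/18 split and the prevalence. Everything on precision and power also rests on the assumed effect of the factor on change, for which the protocol gives no value. If that effect is zero, nothing is gained.

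**What to change.** **Randomization and blinding; Generation and hiding of sequences.** Stratify by one binary factor known at baseline, for example pelvic radiotherapy yes/no, taken from the type of oncological treatment. Use one permuted-block list per stratum with mixed block sizes. This also keeps the arms close to 18 each.

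**Statistical Analysis.** Pre-specify that factor together with its factor-by-time term for each outcome, without group-by-factor terms. A factor term in a change-score model does the same job exactly. An ANCOVA of the post score on baseline, group and factor serves the same purpose. A factor main effect alone does not.

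**If allocation is already done,** make only the model change and fix it before the arms are compared. It then gains precision at 0.5 SD or more, and roughly breaks even or loses slightly at 0.3 SD. Its main value in that case is that the adjustment is settled in advance.

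**Cost:** two short lists instead of one, 1 df, a sentence in each section, and confirmation of the stratum before each assignment. Keep to one factor. With the same f = 0.2 and correlation of 0.64, coding type, stage and treatment in full at 3 to 5 df would lower power from 78.5% to about 74 or 71% if they explained nothing.

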### **Blinding (masking)**

Outcome assessments before and after the intervention will be performed by a physical therapist blinded to the allocation of participants in each group.

### **Data collection**

Standardized forms will be used to record pre- and post-intervention evaluations. The registry will consider demographic data, social and health habits, clinical variables: comorbidities, blood pressure, body mass index (weight, height), type of gynecological cancer, cancer staging and type of oncological treatment. In addition, the dosage of the kinesthetic intervention will be recorded according to the Borg scale for each session.

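### The plan makes no provision for collecting or analysing harms, so the tolerability of the added hypopressive block cannot be reported by arm

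*Combined protocol and SAP*

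**What the plan says.** The Data collection section is the only list of what is recorded. Standardized forms cover the evaluations at the start and end. The list then continues: "The registry will consider demographic data, social and health habits, clinical variables: comorbidities, blood pressure, body mass index (weight, height), type of gynecological cancer", followed by stage and oncological treatment. The only item recorded at every session is exercise dosage: "the dosage of the kinesthetic intervention will be recorded according to the Borg scale for each session".

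The Protocol of therapeutic exercise section adds that, besides Borg, "respiratory rate and heart rate will be monitored, considering instructions via remote". It sets the weekly format as "three times a week, twice in a synchronous online way and once in an asynchronous way". It also says that the exercise sessions are the same in both groups. The Hypopressive Exercise Protocol section then adds a block at the end of the session in one group only, delivered "without performing the apnea, to guarantee the safety of the user and that the intervention is remote".

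Under Blinding (masking): "Outcome assessments before and after the intervention will be performed by a physical therapist blinded to the allocation of participants in each group". Under Statistical Analysis: "To assess fatigue, symptoms of urinary incontinence, sexual function and quality of life, a two-way mixed analysis (two-way ANOVA) will be performed". No section defines, collects, reports or tabulates adverse events, shortened sessions or reasons for stopping.

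**The concern.** Safety was on the designers' minds: the experimental exercise was modified for that reason and because delivery is remote. The hypopressive block is also what separates the arms, so whether women tolerate it is a basic question for anyone who reads the result. Yet the planned data contain nothing from which tolerability could be described by arm, apart from the efficacy scores at the final visit.

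This is more than missing wording. An analyst can repair an unclear model after the fact, but cannot recover symptoms that nobody asked about. A report from this trial could say neither how many women in each arm had a new or worse symptom, nor how many sessions were stopped early and in which block, nor why a woman gave up training.

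**Working it through.** The plan gives no figure on harms to reproduce. The check is a reading of every section, followed by simple arithmetic on how much exposure goes unrecorded and what a record could show.

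**Step 1. Can each kind of harm be found in the planned data?**

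| Kind of harm | Planned source | Captured by arm? |
|---|---|---|
| Worsening in one of the four outcome domains that lasts to the final assessment | Evaluations at start and end, analysed by group and time | Yes, if the woman is assessed at the end |
| Worsening in those domains that resolves before the final assessment | None | No |
| Other adverse events, for example pain or injury | None named | No |
| Session cut short, and why | None; Borg is recorded as dosage | No |
| Reason for stopping training | None | No |

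Remote monitoring of heart and respiratory rate does not change the table. No event or threshold is attached to these signs, the recording list omits them, and leakage or pain would not show in them.

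**Step 2. Exposure without a harm item.** Inputs: 4 weeks and 3 sessions a week (Generation and hiding of sequences); 36 women, 18 per group (Determination of sample size); 1 of 3 weekly sessions asynchronous (Protocol of therapeutic exercise). Full enrolment and attendance are assumed.

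- Sessions per woman: 4 × 3 = 12. In total: 12 × 36 = 432. In the hypopressive arm: 12 × 18 = 216.
- Asynchronous sessions per woman: 4 × 1 = 4. In total: 4 × 36 = 144. In the hypopressive arm: 4 × 18 = 72.

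These counts measure exposure, not consequence. All 12 sessions fall between only two outcome assessments.

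**Step 3. What a record could show.** The chance that at least one of 18 women is affected is 1 − (1 − p)^18. The documents give no event risk, so p is an assumption, shown over a range:

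| Assumed risk p | Chance of at least one affected among 18 |
|---|---|
| 1% | 17% |
| 5% | 60% |
| 10% | 85% |
| 20% | 98% |

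**Step 4. What zero events would mean.** The exact two-sided 95% upper limit for 0/n is 1 − 0.025^(1/n).

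- n = 18: 1 − 0.025^(1/18) = 0.185, or 18.5%.
- n = 36: 1 − 0.025^(1/36) = 0.097, or 9.7%.

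The one-sided limits, 1 − 0.05^(1/n), are 15.3% and 8.0%. The two-sided values are the ones that match a 95% confidence interval. Collection would therefore probably pick up a common problem, but could neither exclude a fairly frequent one nor support a formal test between arms.

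**The case against.** The strongest reply is that the document is short and silence is not prohibition. The list under Data collection cannot be exhaustive: two signs monitored in every session are missing from it, so staff may well note events too. The outcome domains are themselves where harm from this programme might appear, and they are measured by a blinded assessor and compared by arm. With 18 women per arm, harm data would be descriptive at best.

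Much of this stands, and it limits what may be said. Several stronger readings are tempting, but the documents do not support them:

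- A reader might infer that the trial will end with no harm data by arm. Lasting worsening in the four domains is captured, and informal notes are not ruled out. What can be said is that the plan does not provide for harms collection.
- A reader might infer that a woman who stops in week 2 leaves only Borg values. Her baseline evaluation precedes randomization, and no section says she would miss the final assessment.
- A reader might take the safety phrase in the Hypopressive Exercise Protocol as a claim about results. It gives the purpose of leaving out the apnea.
- A reader might assume that a session form already exists. Standardized forms are tied only to the evaluations at the start and end; for Borg the text says only that it is recorded.
- A reader might expect harm fields to remove bias from selective dropout. They would help describe it, but the efficacy comparison would still depend on how missing outcomes are handled.

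The reply does not fill the gap. Informal notes have no definition, no schedule and no assurance of equal ascertainment in the two arms. One session in three is asynchronous, with no live contact described.

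**Conclusion.** The point holds as a gap in provision. The plan neither collects nor analyses harms beyond what the four outcome domains show at the final assessment. Transient symptoms, other adverse events, shortened sessions and reasons for stopping have no planned record, so the tolerability of the hypopressive block cannot be reported by arm.

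The size is up to 432 sessions without a harm item, 216 of them in the hypopressive arm, assuming 36 women and full attendance. Even complete collection with no events would leave upper limits of 18.5% per arm and 9.7% overall. The efficacy analysis, sample size and significance level are not affected. The plan should be changed before training starts, because these data cannot be reliably reconstructed afterwards.

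The conclusion rests on the text of the protocol and analysis sections. Nothing is inferred from the missing figure or the removed consent pages.

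**What to change.** In the Data collection section, add three items to the per-session recording, worded and asked identically in both arms:

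1. Any new or worse symptom since the last contact, including urinary leakage and pain.
2. Whether the session was cut short, in which block, and why.
3. The reason, if training is stopped.

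For the weekly asynchronous session, ask these questions at the next synchronous contact. If an asynchronous session comes last, make a separate contact before the final assessment. Someone other than the blinded assessor should record the answers, since they could reveal the group. Continue until the post-intervention assessment, including for women who have stopped training.

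In the Statistical Analysis section, add a descriptive table by arm: the number of women with at least one event, with exact two-sided 95% confidence intervals, and the counts of shortened sessions and reasons for stopping. State that no formal comparison of harms between arms is planned.

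The cost is roughly a minute per session (an estimate, since the documents do not describe the recording tool) and one extra table. Sample size, significance level and exercise content stay as they are.
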